10.10.2 Investigator Reporting: Notifying the Penn IRB

This section describes the requirements for safety reporting by investigators who are Penn faculty, affiliated with a Penn research site, or otherwise responsible for safety reporting to the Penn IRB. The University of Pennsylvania IRB (Penn IRB) requires expedited reporting of those events related to study participation that are unforeseen and indicate that participants or others are at increased risk of harm. The Penn IRB will not acknowledge safety reports or bulk adverse event submissions that do not meet the criteria outlined below. The Penn IRB requires researchers to submit reports of the following problems within 10 working days from the time the investigator becomes aware of the event:

Any adverse event (regardless of whether the event is serious or non-serious, on-site or off-site) that occurs any time during or after the research study, which in the opinion of the principal investigator is:

Unexpected (An event is “unexpected” when its specificity and severity are not accurately reflected in the protocol-related documents, such as the IRB-approved research protocol, any applicable investigator brochure, and the current IRB-approved informed consent document and other relevant sources of information, such as product labeling and package inserts.)

Version: 11/24/2020

CONFIDENTIAL

This material is the property of the University of Pennsylvania

AND

Related to the research procedures (An event is “related to the research procedures” if in the opinion of the principal investigator or sponsor, the event was more likely than not to be caused by the research procedures.)

Reporting Process

Unanticipated problems posing risks to subjects or others as noted above will be reported to the Penn IRB using the form: “Unanticipated Problems Posing Risks to Subjects or Others Including Reportable Adverse Events” or as a written report of the event (including a description of the event with information regarding its fulfillment of the above criteria, follow-up/resolution and need for revision to consent form and/or other study documentation).

Copies of each report and documentation of IRB notification and receipt will be kept in the Clinical Investigator’s study file.

Other Reportable Events:

For clinical drug trials, the following events are also reportable to the Penn IRB:

Any adverse experience that, even without detailed analysis, represents a serious unexpected adverse event that is rare in the absence of drug exposure (such as agranulocytosis, hepatic necrosis, Stevens-Johnson syndrome).

Any adverse event that would cause the sponsor to modify the investigators brochure, protocol or informed consent form, or would prompt other action by the IRB to assure protection of human subjects.

Information that indicates a change to the risks or potential benefits of the research, in terms of severity or frequency.

For example:

An interim analysis indicates that participants have a lower rate of response to treatment than initially expected.

Safety monitoring indicates that a particular side effect is more severe, or more frequent than initially expected.

A paper is published from another study that shows that an arm of your research study is of no therapeutic value.

Change in FDA safety labeling or withdrawal from marketing of a drug, device, or biologic used in a research protocol.

Breach of confidentiality

Change to the protocol taken without prior IRB review to eliminate apparent immediate hazard to a research participant.

Incarceration of a participant when the research was not previously approved under Subpart C and the investigator believes it is in the best interest of the subject to remain on the study.

Complaint of a participant when the complaint indicates unexpected risks or the complaint cannot be resolved by the research team.

Protocol violation (meaning an accidental or unintentional deviation from the IRB approved protocol) that in the opinion of the investigator placed one or more participants at increased risk, or affects the rights or welfare of subjects.

10.10.3 Abramson Cancer Center Data Safety Monitoring Committee (DSMC):

Every effort should be made to report an event as a diagnosis, not as a list of symptoms. Symptoms that led to the diagnosis should be included in the event description, but should not be the actual event.

Version: 11/24/2020

CONFIDENTIAL

This material is the property of the University of Pennsylvania

On-Site subjects (this includes any subjects enrolled at other sites on an ACC multi-site study). Only events on studies categorized as HIGH risk based on the ACC Risk table must be submitted to the DSMC as follows:

All grade 3 or higher events regardless of attribution or expectedness within 10 business days of knowledge.

All unexpected deaths within two business day of knowledge.

All others deaths within 30 days of knowledge. Deaths of subjects greater than 90 days from the last study treatment/intervention are not reportable unless a longer time frame is specified in the protocol.

Study PIs have the option to request DSMC review of AEs that do not meet the high risk definition if they would like an independent opinion of the event. The DSMC review will be limited to the scope specifically requested by the PI.

All events must be entered into the ACC Clinical Trials Management System (CTMS using the centralized reporting form).SAEs will be submitted to the DSMC through the Velos Clinical Trial Management System. Once an event is reported, you must keep the information accurate and current in Velos.

Exception

A one time, intentional action (planned prospectively) or process that departs from the IRB and CTSRMC approved study protocol, intended for one occurrence. Advance documented IRB and DSMC approval is required.

For in-house studies with a Medical Monitor or Safety Monitoring Committee (not DSMB), approval must be obtained from the Medical Monitor or Safety Monitoring Committee prior to submitting your exception request to the DSMC.

The following information must be contained in your exception request:

- When it is needed and why it is needed in that timeframe
- Has the Medical Monitor or Sponsor approved and provide the documentation of approval
- Is this an exception from eligibility, treatment, disease progression, study calendar windows, etc.
- Why the exception is needed (cite the section(s) of the protocol) along with the full clinical details of the subject. This must be determined by the sub-Investigator or PI.
- The reason why the protocol currently doesn't allow the situation for which an exception is being requested. This must be determined by the sub-Investigator or PI.
- If there are plans to amend the protocol and if not, why not.
- If additional follow-up or interventions will be required in order to protect the subject as a result of this exception.

Study Exceptions the DSMC may Reject:

Exceptions to eligibility, treatment/dosing, contraindicated treatment/therapies/interventions or safety tests for the following types of studies may be rejected by the DSMC:

- Any investigator-initiated treatment study.
- Any treatment study involving on-campus manufacturing of any component, regardless of sponsor.

To seek approval, you must provide the DSMC with strong and compelling scientific and clinical information to support your request. You should also include a statement explaining whether or not the protocol will be amended.

If the protocol will not be amended your reasoning must be provided. If this situation is likely to happen again, the DSMC will require a protocol amendment.

Deviation

Any unintentional action or process that departs from IRB approval and is identified retrospectively. The deviation is reportable to the DSMC and the IRB within 10 days from the time the event becomes known to the study team only when: one or more participants were placed at increased risk of harm, or, the event has the potential to occur again, or the event has the potential to qualify as serious or continuing noncompliance.

If the PI determines that a deviation has **any potential** to impact participant safety (harm and/or risk), or the integrity of data produced from the participant, or some other overall impact on the study, the PI must report the deviation to the IRB and DSMC as described above. The IRB will make the final assessment of the impact. The DSMC will assess for additional safety and scientific integrity concerns.

The following information must be contained in your deviation report:

- When it happened? When the study team (any member) became aware
- The full description of the deviation including important dates, test results, actions taken towards the subject, etc. Also, why it happened and how it was identified.
- Was the Medical Monitor or Sponsor notified. If so, their response?
- The PIs assessment of the impact on risk, safety and/or outcome. If no impact, why. If impact, what and what will happen next.
- The corrective actions that have been implemented to date and the impact of those corrective action plans.
- Future corrective action plans (if applicable) and the impact of those plans.
- If there are plans to amend the protocol (if applicable to prevent future deviations) and if not, why not.

If the PI determines that the event had no potential to impact participant safety (harm and/or risk) or the integrity of data produced from the participant, the PI must fully document his/her rationale for each category (risk, harm, and participant data).

11.0 Data Handling and Record Keeping

11.1 Confidentiality

Information about study subjects will be kept confidential and managed according to the requirements of the Health Insurance Portability and Accountability Act of 1996 (HIPAA). Those regulations require a signed subject authorization informing the subject of the following:

- What protected health information (PHI) will be collected from subjects in this study
- Who will have access to that information and why
- Who will use or disclose that information
- The rights of a research subject to revoke their authorization for use of their PHI

In the event that a subject revokes authorization to collect or use PHI, the investigator, by regulation, retains the ability to use all information collected prior to the revocation of subject authorization. For subjects that have revoked authorization to collect or use PHI, attempts should be made to obtain permission to collect at least vital status (i.e. that the subject is alive) at the end of their scheduled study period

11.2 Data Collection and Management

This study will use Velos as the data management system. The study case report form (CRF) is the primary data collection instrument for the study and will be electronically created and completed in Velos. CRFs will be provided for each patient. Subjects must not be identified by name on any CRFs. Subjects will be identified by their patient identification number (PID). All data requested on the CRF must be recorded. All missing data must be explained. If a space on the CRF is left blank because the procedure was not done or the question was not asked, write “N/D”. If the item is not applicable to the individual case, write “N/A.”.)

12.0 Study Monitoring, Auditing, and Inspecting

12.1 Study Monitoring

It is the responsibility of the Principal Investigator to oversee the safety of the study at his/her site. This safety monitoring will include careful assessment and appropriate reporting of adverse events as noted above, as well as the construction and implementation of a site data and safety-monitoring plan. Medical monitoring will include a regular assessment, at least every 6 months, of the number and type of serious adverse events by an independent clinician, [name], Department of Medicine, Division of Hematology-Oncology. Additionally, the Medical Monitor will be consulted for protocol exceptions and deviations and as needed for decision-making regarding dose modifications, study eligibility, and any need to stop enrollment or the study for safety concerns.

This study will be monitored in accordance with the Cancer Center’s Clinical Trials Scientific Review and Monitoring Committee (CTSRMC) Plan, approved by NCI during the Core Grant’s most recent review. This plan requires that the investigator submit a study-specific plan outlining how data will be reviewed. In addition, the CTSRMC plan calls for an internal audit by the Cancer Center’s Data Safety Committee twice yearly. The investigator will allocate adequate time for such monitoring activities. The Investigator will also ensure that the monitor or other compliance or quality assurance reviewer is given access to all the above noted study-related documents and study related facilities (e.g. pharmacy, diagnostic laboratory, etc.), and has adequate space to conduct the monitoring visit.

12.2 Auditing and Inspecting

The investigator will permit study-related monitoring, audits, and inspections by the IRB, government regulatory bodies, and University compliance and quality assurance groups of all study related documents (e.g. source documents, regulatory documents, data collection instruments, study data etc.). The investigator will ensure the capability for inspections of applicable study-related facilities (e.g. pharmacy, diagnostic laboratory, etc.).

Participation as an investigator in this study implies acceptance of potential inspection by government regulatory authorities and applicable University compliance and quality assurance offices.

13.0 Ethical Considerations

This study is to be conducted according to US and international standards of Good Clinical Practice (FDA Title 21 parts 50 and 56 and International Conference on Harmonization guidelines), applicable government regulations and Institutional research policies and procedures.

This protocol and any amendments will be submitted to a properly constituted independent IRB, in agreement with local legal prescriptions, for formal approval of the study conduct.

All subjects for this study will be provided a consent form describing this study and providing sufficient information for subjects to make an informed decision about their participation in this study. This consent form will be submitted with the protocol for review and approval by the IRB and CTSRMC for the study. The formal consent of a subject, using the IRB-approved consent form, must be obtained before that subject undergoes any study procedure. The consent form must be signed by the subject and the investigator-designated research professional obtaining the consent.

14.0 Study Finances

14.1 Funding Source

This clinical study, including correlative work, will be supported by funds provided by Bristol-Myers Squibb.

14.2 Conflict of Interest

All University of Pennsylvania Investigators will follow the University of Pennsylvania Policy on Conflicts of Interest Related to Research.

15.0 Publication Plan

Neither the complete nor any part of the results of the study carried out under this protocol, nor any of the information provided by the sponsor for the purposes of performing the study, will be published or passed on to any third party without the consent of the study sponsor. Any investigator involved with this study is obligated to provide the sponsor with complete test results and all data derived from the study.

17.0 Schedule of Events

Note: study timepoints may be performed within a +/- 3 day window.

	Screening ¹	Cycle 1 (56 days)		Cycles 2+ (56-day cycles)		End of Study Visit	Follow -up
		1	10- 14	29	1	29	
Treatments							
Nivolumab		X		X	X	X	
Ipilimumab		X			X		
Tests and Observations							
Informed Consent ²	X						
Medical History	X						X ⁶
Physical Exam and Performance Status	X	X			X	X	X
AE Assessment		X		X	X	X	X
CBC w/ differential	X	X		X	X	X	X
Serum Chemistry ⁴	X	X		X	X	X	X
TSH	X				X	X	X
CEA ⁸	X	X		X	X	X	X
Pregnancy test ⁵	X	X		X	X	X	X
Disease Assessment (routine CT/MRI) ³	X				X		X ⁷
Research Correlates							
Tumor biopsy	X		X				
Research Blood (60mL)	X ⁹		X	X	X		X

¹ Laboratory screening evaluations (section 4.1 #7) are to be conducted within 14 days prior to start of protocol therapy or should be repeated on cycle 1 day 1 prior to treatment to confirm eligibility. Baseline disease assessment with imaging must be conducted within 21 days prior to start of protocol therapy. Screening procedures may also occur on cycle 1 day 1 prior to therapy.

² Informed consent will be documented prior to initiation of any other research related activity. If there have been tests/procedures that have been performed as part of subjects work-up or routine practice prior to informed consent and within the screening evaluation window then those tests/procedures do not have to be repeated

³ CT/MRI, and/or PET/CT in the event that PET/CT is determined to be standard of care.

⁴ Sodium, potassium, BUN, serum creatinine, calcium, glucose, AST, ALT, total bilirubin, alkaline phosphatase, albumin

⁵ Within 72 hours prior to first dose of cycle 1 immunotherapy. Men and women of childbearing potential must agree to use a medically accepted form of birth control (see Appendix A) OR must agree to completely abstain from intercourse for two weeks before beginning study treatment, during participation in this study, and for 5 months (women) or 7 months (men) after the final study treatment.

⁶Limited to following of survival and disease recurrence through review of the medical record for up to 3 years after the end of study visit (every 6 months for the first year, then annually for the second two years).

⁷MRI/CT scan will be performed at frequency determined by clinical care with data to be collected from the medical record for the purposes of the research.

⁸CEA will be repeated with each cycle if abnormal at screening

⁹Research blood is to be drawn on the same day as the tumor biopsies during screening and cycle 1 days 10-14. It should not be drawn at the initial screening visit. If the biopsy is omitted, research blood draw is still required and can occur during screening window or on cycle 1 day 1 prior to treatment. Research blood can be drawn within 3 days before or after biopsy if required for scheduling.

Appendix A: Definition of Non-Childbearing Potential and Medically Acceptable Methods of Birth Control

Non-childbearing potential is defined as any of the following (by other than medical reasons):

1. ≥ 45 years of age and has not had menses for >2 years
2. Amenorrheic for <2 years without a hysterectomy and oophorectomy and a follicle-stimulating hormone value in the postmenopausal range upon pre-study (screening) evaluation
3. Post hysterectomy, oophorectomy or tubal ligation. Documented hysterectomy or oophorectomy must be confirmed with medical records of the actual procedure or confirmed by imaging. Tubal ligation must be confirmed with medical records of the actual procedure otherwise the patient must be willing to use 2 other adequate methods.

Females:

Women of child-bearing potential must agree to use 2 of the following forms of contraception OR completely refrain from intercourse during the study and for at least 5 months following the last dose of study drug.

Males:

Men with partners of child-bearing potential must agree along with their partner to use 2 of the following forms of contraception OR completely refrain from intercourse during the study and for at least 7 months following the last dose of study drug.

Acceptable methods include:

- Condoms
- Diaphragm
- Cervical cap
- Intra-uterine device
- Surgical sterilization (tubal ligation or vasectomy)
- Oral contraceptives

Abstinence at certain times of the cycle, such as during ovulation or after ovulation, or withdrawal are not acceptable methods. The list of methods above is not exhaustive and additional contraception methods may also be acceptable. The study doctor must approve the contraceptive methods in subjects with child-bearing potential.

[figure not shown]

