1.2 Secondary Objectives

1. To determine overall response rate, duration of response, and progression-free survival by iRECIST and RECIST 1.1. To determine overall survival.
2. To determine the toxicity rates by CTCAE v 5.0

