2.5 Safety of Nivolumab and Ipilimumab

The combination of nivolumab and ipilimumab has the potential for increased frequencies of AEs compared to ipilimumab monotherapy or nivolumab monotherapy. The toxicity profile of the nivolumab + ipilimumab combination has been shown to correlate with the ipilimumab dose: with increasing doses of ipilimumab, there has been an increase in frequency of AEs and, potentially, the severity of these events; however, no novel toxicities have been demonstrated versus either agent alone. In the current regimen for this protocol, the dose of ipilimumab will be cumulatively lower than the approved dose level for the combination for the treatment of advanced and metastatic melanoma. The toxicity profile with lower doses of ipilimumab has been established to be very similar to that of nivolumab monotherapy as detailed below in section 2.6.

The most common (reported at > 10% incidence) treatment related AEs with the combination are fatigue, rash, pruritus, diarrhea, lipase increased, pyrexia, ALT increase, AST increased, amylase increased and vitiligo. These classes of AEs are expected for the combination of nivolumab and ipilimumab based on the known AE profile of each drug alone. In addition, many of the Grade 3-4 AEs are laboratory in nature (ie, LFTs, lipase, amylase), occur without clinical sequelae, and are been manageable and reversible following intervention dose delays or with systemic steroid treatment. However, immune AEs have the potential to be fatal if not detected early and managed per the established algorithm, and fatal AEs have been reported for both ipilimumab and nivolumab monotherapy. Adverse drug reactions with fatal outcome in clinical trial participants treated with nivolumab monotherapy and nivolumab and ipilimumab combination therapy are listed in the current version of the nivolumab investigator brochure (IB).

A pattern of immune-related AEs has been defined, for which management algorithms have been developed; these are provided in Appendix B. Most high-grade events are manageable with the use of corticosteroids or hormone replacement therapy (endocrinopathies) as instructed in these algorithms.

[figure not shown]

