7.2 Assessment of Laboratory Measures and Disease Progression

7.2.1 Laboratory Safety Monitoring

CBC with differential will be assessed at screening, on days 1 and 29 of each treatment cycle, and at the end of treatment visit. Serum pregnancy will be assessed for women of childbearing potential at screening and every 4 weeks. Non-childbearing potential is defined in Appendix A. Serum chemistry labs will be assessed at screening, on days 1 and 29 of each treatment, and at the end of treatment visit. Serum TSH will be assessed at screening, on day 1 of cycle 2 and all subsequent cycles, and at the end of treatment visit.

For all laboratory measures, a window of +/- 3 days is acceptable.

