8.1.9 Side Effects

Version: 11/24/2020

CONFIDENTIAL

This material is the property of the University of Pennsylvania

- Cardiovascular: Edema, peripheral edema, ventricular arrhythmia, pulmonary embolism, vasculitis
- Central nervous system: Fatigue, headache, peripheral neuropathy, peripheral sensory neuropathy, dizziness, peroneal nerve palsy, motor dysfunction, migraine, myasthenia, encephalitis, facial paralysis, Guillain-Barré syndrome, neuropathy
- Dermatologic: Skin rash, pruritis, vitiligo, exfoliative dermatitis, erythema, erythema multiforme, psoriasis, urticarial, palmar-plantar erythrodysesthesia
- Endocrine and metabolic: Hyponatremia, increased serum triglycerides, hyperkalemia, increased thyroid stimulating hormone level, hypocalcemia, increased serum cholesterol, hypercalcemia, hypothyroidism, hypomagnesemia, hypokalemia, hyperglycemia, hyperthyroidism, adrenocortical insufficiency, diabetes mellitus, diabetic ketoacidosis, weight loss, hypophysitis, pituitary insufficiency
- Gastrointestinal: Diarrhea, colitis, decreased appetite, increased serum lipase, nausea, constipation, vomiting, increased serum amylase, abdominal pain, duodenitis, gastritis, pancreatitis
- Hematologic: Lymphocytopenia, anemia, neutropenia, thrombocytopenia
- Hepatic: Increased serum AST, increased serum ALT, increased serum alkaline phosphatase, increased serum bilirubin, hepatitis, hepatic failure
- Immunologic: Antibody development
- Neuromuscular and skeletal: Weakness, musculoskeletal pain, back pain, arthralgia, spondyloarthropathy, limb pain, polymyalgia rheumatica
- Renal: Increased serum creatinine, renal disease, nephritis, renal insufficiency
- Respiratory: Upper respiratory tract infection, productive cough, cough, dyspnea, dyspnea on exertion, bronchopneumonia, pneumonia, pleural effusion, pneumonitis, respiratory failure, pneumonia due to *Pneumocystis jiroveci*
- Ophthalmic: Iridocyclitis, iritis
- Miscellaneous: Fever, infusion related reactions, hypersensitivity reaction, sarcoidosis

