9.1.2.5 Safety Analysis

Safety analysis will be performed on the safety – evaluable population, defined as all enrolled subjects who received at least one dose of study treatment. Summaries of AEs, SAEs, deaths, changes in laboratory test results, vital signs and exposure to study drug will be presented. Drug exposure will be summarized to include treatment duration, number of doses and dose intensity. Laboratory data with values outside reference ranges will be summarized by NCI-CTCAE v 5.0 grades.

We will conduct a Bayesian toxicity monitoring plan every 3 patients with a target discontinuation rate due to toxicity of 30%. We assume a *Beta*(1,2) prior, equivalent to one discontinuation of treatment (both ipilimumab and nivolumab) due to toxicity in 3 treated patients. Early study termination for toxicity will be considered based on a posterior probability that the rate of treatment discontinuation due to toxicity exceeds 30%. Early termination will be considered if treatment discontinuation due to toxicity occurs in 2 of 3 patients (0.84 posterior probability), 3 of 6 patients (0.81), 4 of 9 patients (0.79), 5 of 12 patients (0.78), or 6 of 15 patients (0.78).

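### Lipase and amylase rises are named as common and as grade 3-4 toxicities of the combination, but no scheduled test measures them, so the CTCAE toxicity rates will tend to understate them

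*Combined protocol and SAP*

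**What the plan says.** Section 1.2 sets a secondary objective: "To determine the toxicity rates by CTCAE v 5.0". The Statistical Methodology entry of the Study Summary promises these rates by category with 95% confidence intervals. Section 9.1.2.5 takes everyone dosed at least once as the safety population and adds a laboratory summary: "Laboratory data with values outside reference ranges will be summarized by NCI-CTCAE v 5.0 grades".

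Section 2.5 describes what to expect. It introduces its list as "The most common (reported at > 10% incidence) treatment related AEs with the combination" and names "fatigue, rash, pruritus, diarrhea, lipase increased, pyrexia, ALT increase, AST increased, amylase increased and vitiligo". It then says that "many of the Grade 3-4 AEs are laboratory in nature (ie, LFTs, lipase, amylase), occur without clinical sequelae". The side-effect list for nivolumab in Section 8.1.9 includes "increased serum lipase" as well as raised amylase and pancreatitis, and Section 8.2.9 repeats these for ipilimumab.

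Section 7.2.1 gives the timing: "Serum chemistry labs will be assessed at screening, on days 1 and 29 of each treatment, and at the end of treatment visit". Footnote 4 of the Schedule of Events fixes the content of that chemistry: "Sodium, potassium, BUN, serum creatinine, calcium, glucose, AST, ALT, total bilirubin, alkaline phosphatase, albumin".

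**The concern.** Section 2.5 picks out three kinds of laboratory toxicity: liver function tests, lipase and amylase. The panel covers the first and omits the other two. If many of these rises have no clinical consequences, as Section 2.5 says, little would prompt a physician to order the test. Yet the planned rates divide by everyone treated, whether tested or not.

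The secondary toxicity objective is what is at stake. For these two enzymes a rate would partly reflect how often somebody ordered the test. Any overall grade 3-4 rate would carry the same downward error, and a reader could set it beside reports in which the enzymes were measured without knowing that it is not comparable.

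**Working it through.** **Is either enzyme measured on schedule?**

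- Footnote 4 of Section 17.0 lists 11 analytes. AST, ALT, bilirubin and alkaline phosphatase are there; lipase and amylase are not.
- Section 7.2.1 schedules blood count, chemistry, TSH and pregnancy testing. Section 17.0 adds CEA and research blood.
- The eligibility laboratory tests (Section 4.1, item 7) include neither enzyme, so no baseline value is planned.

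No scheduled test measures them.

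**How could a rise reach the data?** Only through a test ordered off schedule. From there the routes differ:

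- As an adverse event, it must also pass Section 10.6: an isolated laboratory abnormality counts only if it changes study drug, needs intervention, or is judged important by the investigator.
- In the graded laboratory summary of Section 9.1.2.5, no such filter applies, but the value must exist.

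**Illustration of size.** The plan gives no lipase or amylase rate for this regimen, so there is no planned figure to reproduce. Inputs:

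- n = 21, the planned number of subjects.
- True rate p of any-grade rise: 10% (the threshold in Section 2.5, used as an assumption) and 20% (assumption).
- Share s of rises found off schedule: 10%, 25%, 50% (assumption; the documents give none).

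If the enzymes were measured in everyone, the expected number with a rise is n × p. At p = 10% this is 21 × 0.10 = 2.1, and the chance of seeing at least one is 1 − 0.90^21 = 0.89. At p = 20% it is 4.2, with a chance of 1 − 0.80^21 = 0.99.

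With a share s found, the observed rate is p × s, the expected count is n × p × s, and the chance of reporting none is (1 − p × s)^21:

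| p | s | Observed rate | Expected count | Chance of none |
|---|---|---|---|---|
| 10% | 10% | 1.0% | 0.21 | 81% |
| 10% | 25% | 2.5% | 0.53 | 59% |
| 10% | 50% | 5.0% | 1.05 | 34% |
| 20% | 10% | 2.0% | 0.42 | 65% |
| 20% | 25% | 5.0% | 1.05 | 34% |
| 20% | 50% | 10.0% | 2.10 | 11% |

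Since the observed rate is p × s, the proportional shortfall depends only on s. A lower true rate changes the counts but not the direction.

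If nobody were tested and a row were printed, it would read 0/21, with an exact 95% upper limit of 1 − 0.025^(1/21) = 16.1%. That limit reflects sampling error under full measurement and says nothing about absent measurement.

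**What is not affected.** The primary test uses progression data only. Its stated 81% power reproduces by the normal approximation: (0.23 − 1.645 × √(0.17 × 0.83/21)) / √(0.40 × 0.60/21) = 0.89, and Φ(0.89) = 0.813. The Bayesian rule in Sections 9.1.2.5 and 10.9 counts discontinuation of both drugs for toxicity, which an unnoticed enzyme rise would rarely cause.

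**The case against.** The best case for the plan has four parts.

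First, Section 10.6 would keep many silent rises out of the adverse event counts even if both enzymes were measured at every visit. This stands, and it means that 2.1 of 21 is a count of rises, not of adverse events lost. It does not reach the laboratory summary in Section 9.1.2.5, which is by grade and carries no such filter.

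Second, the figure above 10% has no grade attached and describes the combination generally. Section 2.5 itself says that toxicity rises with ipilimumab dose, that this regimen gives cumulatively less than the approved melanoma combination, and that low-dose toxicity resembles nivolumab alone. A reader might take 10% as the protocol's own minimum for this trial; the text does not support that, and the true rate may be lower. Still, Section 8.1.9 lists both enzyme rises for nivolumab itself, so the events remain expected.

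Third, off-schedule testing is not barred, and Section 6.0 leaves the management of toxicity to the treating clinician. The Appendix B algorithm figures are not reproduced in the text available, so any work-up they advise cannot be checked. A reader might infer that the plan cannot detect these events, or that their rates must come out near zero. Neither follows: the result depends on how often the tests are ordered. Nor do the documents say that a 0% row with an interval will be printed for an analyte that was never drawn.

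Fourth, omitting a test for rises described as having no clinical consequences is a defensible monitoring choice. That is right, and the point here does not require routine testing. It requires that the reported rates match what was measured.

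**Conclusion.** The point holds as a problem of ascertainment in a stated secondary objective. Followed as written, the plan will tend to understate lipase and amylase toxicity in the all-treated rates and in any overall grade 3-4 rate. The graded laboratory summary will lack these enzymes for every subject not tested.

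The direction is clear; the size is not. The illustrative observed rate of 1% to 5% rests on an assumed 10% true rate, an assumed 10% to 50% found, and 21 subjects. The safety denominator may exceed 21, because Section 4.3.1 replaces subjects not evaluable for efficacy while they still count for toxicity. The documents give no grade 3-4 rate for either enzyme, so the effect on an overall grade 3-4 rate cannot be computed.

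**What to change.** Reconcile Section 2.5, Section 9.1.2.5 and footnote 4 of Section 17.0.

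At minimum, amend Section 9.1.2.5 to:

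- state that lipase and amylase are not systematically assessed;
- report any rises as counts together with the number of subjects tested, with no all-treated rate or confidence interval;
- show the overall grade 3-4 rate with and without them.

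This costs a short text change and a count of who was tested.

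If the sponsor wants these rates to be part of the toxicity objective, the alternative is to run both analytes on the chemistry blood already drawn, including at screening so that a baseline exists. That needs no new visit; it brings a small laboratory cost and some incidental findings to review. Whether to test routinely is a clinical monitoring choice for the sponsor.
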